RCT. The final phase of the proposed project will implement an RCT to examine whether the program is feasible and associated with improvements in the treatment targets (see Measures and Figure 1). Thirty-six siblings will be recruited and randomly assigned to participate in Siblings FORWARD (N=18) or receive written materials about future planning (N=18). Siblings assigned to Siblings FORWARD will complete Time 1 (pre-program) measures, participate in the 6-session intervention over 4 months, complete Time 2 measures immediately after program completion, and complete Time 3 measures 3 months later. Those assigned to the control condition will complete Time 1 measures at the time of enrollment, Time 2 measures 4 months after enrollment, and Time 3 measures 7 months after enrollment. With the exception of the clinician rating of the sibling's ASD symptoms (see Measures), all data will be collected by the Boston University study team via home visits in order to separate data collection from the Arc providers. Adults with ADS and their families will determine whether the adult with ASD can complete the questionnaires (see Methods). When possible, the adult with ASD will complete the measures independently in the presence of a Boston University research team member. These measures can also be completed with the support of a research team member, sibling, parent, or service provider. Given possible geographic separation, sibling data will be collected via mailed questionnaire packets. We will track this data collection method to inform future data collection logistics.

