#### Baseline Characteristics (Measured at Time 1)

1. Demographics. Family demographic questions include race/ethnicity, gender, family membership (age and gender of siblings), family income, native language, education and employment, and type and size of community. This information will be collected for the adult with ASD, sibling, and parent (when known).
2. Adult with ASD: Autism Symptom Severity. Siblings will rate their brother/sister's ASD symptoms using the Current form of the Social Communication Questionnaire (SCQ). The SCQ is a 40-item proxy-report measure used to assess the presence of specific autistic behaviors. The items represent three areas of functioning: reciprocal social interaction, language and communication, and repetitive and stereotypical behaviors, where higher scores indicate more severe behaviors. The SCQ has established psychometric properties in children and adults and has good reliability and convergent validity. The SCQ manual provides additional information on factor analyses, item validity, and ROC analyses that support its validity. Psychometric properties are good, with alpha reliabilities ranging from .84 to .93 in older age groups.
3. Adult with ASD: Maladaptive Behaviors. Siblings will rate the severity of maladaptive behaviors exhibited by their brother/sister with ASD using the Scales of Independent Behavior-Revised (SIB-R). The SIB-R Maladaptive Behaviors scale consists of 8 categories of behavior problems divided into 3 domains: internalizing, externalizing, and asocial behavior. Standard algorithms translate the frequency and severity ratings into a general summary score. Reliability and validity have been established. We have used this measure in prior research with adult siblings of individuals with ASD.
4. Adult with ASD: Functional Independence. Siblings will rate their brother/sister's functional independence using the Waisman Activities of Daily Living Scale (W-ADL). The 17 items cover the domains of personal care, housekeeping, and mealtime activities. Each item is rated on a 3-point scale (0=does not perform the task at all; 1=performs the task with help; 2=performs the task independently). Items will be summed for a total score. Good reliability (alpha > .90) has been reported.

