Acceptability (open trial and RCT): Qualitative data about perceptions of program usefulness and value collected during exit interviews with providers and participants will be evaluated using the qualitative methods outlined for Aim 1. Participant understanding of measures and procedures (open trial): Missing data and inconsistent response patterns on measures completed by siblings will be recorded. Data collection time will be calculated descriptively (mean, standard deviation, and range); participant burden associated with completing study measures will be captured qualitatively and summarized using content analysis. Enrollment and retention (RCT): Enrollment will be evaluated by calculating the number of eligible participants who chose to enroll in the trial. Descriptive statistics show the average number of sessions completed by participants and retention and follow-up rates. To assess selective attrition, we will evaluate the demographic and clinical characteristics of participants who completed the program versus those who did not using t-tests and chi squares. Adherence (RCT): Providers' fidelity to the manual will be assessed by evaluating video recordings of sessions against checklists of required components and calculating the percentage of required components that were present in each session; 20% of sessions will be coded for fidelity. Appropriateness of outcome measures (RCT): Psychometric properties of measures (alpha coefficients, means, SDs) and descriptive statistics of change scores from pre- to post-program time points (including confidence intervals) will be calculated.

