*Aim 3: To assess the outcomes of participation in the Siblings FORWARD program.* We will examine whether the program shows promise of being successful with the intended population by conducting two-way repeated measures ANOVAs examining main effects of intervention condition (Siblings FORWARD vs. control) and repeated for assessment (pre- post- and 3-month follow up) on measures for program targets (sibling problem solving skills, family communication, future planning self-efficacy, barriers to future planning, and knowledge of services and family future plans) and proximal outcomes (sibling plan of action and adult with ASD quality of life, perceptions of unmet needs, and family relationships). Post-hoc tests will be used in multiple comparisons between groups and within each group. Effect sizes (Cohen's d) will be calculated using the mean difference of the changes recorded from pre- to post-program. We will also analyze percent change and reliable change. If data are missing, analyses will be performed using the 'last observation carried forward' method for intention-to-treat analysis. We will examine descriptive statistics (mean, SD, confidence intervals) at the participant level for patterns and direction of change on outcome measures. We will conduct intent-to-treat analyses if there is program attrition. Finally, we will examine benefit of the program to control participants who elect to participate in the Siblings FORWARD program using one-way ANOVAs (pre to post-program) on treatment targets and proximal outcomes.

We will conduct a preliminary investigation of potential moderators of program effectiveness, including characteristics of the sibling (BAP), family (income, race/ethnicity, English as the primary language, number of family members with ASD), and adult with ASD (severity of ASD symptoms, problem behaviors, functional independence). We will calculate correlations between these variables and change scores in primary outcome variables, and independent samples t-tests between these variables and program completion status.

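### Aim 3 applies correlations and t-tests to race/ethnicity, a nominal variable; with three or more numbered categories the results depend on arbitrary codes (minor)

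*Combined protocol and SAP*

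**What the plan says.** The last paragraph of Data Analysis, Aim 3, opens: "We will conduct a preliminary investigation of potential moderators of program effectiveness". The candidates are one sibling characteristic (broader autism phenotype), four family characteristics, "family (income, race/ethnicity, English as the primary language, number of family members with ASD", and three characteristics of the adult with ASD (symptom severity, problem behaviors, functional independence).

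Two methods are then given for the whole list: "We will calculate correlations between these variables and change scores in primary outcome variables", and "independent samples t-tests between these variables and program completion status". No variable is excepted, and Aim 3 mentions no indicator coding, grouping, ANOVA or chi-square test for a nominal characteristic.

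Two other places bear on this:

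- Data Analysis, Aim 2 (Enrollment and retention) plans to assess selective attrition by comparing "participants who completed the program versus those who did not using t-tests and chi squares".
- Baseline Characteristics, item 1, says how the variable arises: "Family demographic questions include race/ethnicity, gender, family membership (age and gender of siblings), family income, native language". It gives no race/ethnicity categories and no codes.

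**The concern.** A correlation needs numbers whose order and spacing mean something, or a variable with only two levels. An independent-samples t-test by completion status compares the mean of the listed characteristic between completers and non-completers. Race/ethnicity in three or more categories has no order and no mean. If the categories are numbered so that the stated rule can be run, the numbering enters the answer: a real difference between groups can be missed, or shown with either sign.

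The two halves of the rule differ in exposure. For completion, Aim 2 already plans tests suited to categorical characteristics, so Aim 3 is out of line with the plan's own method. For race/ethnicity against change scores, the documents offer no valid method anywhere. Because Design Considerations & Future Directions foresees closer study of mediators and moderators in larger trials, a coding artefact here could point that work the wrong way.

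**Working it through.** The plan states no alpha, effect size, power or result for this analysis, so there is no figure to reproduce.

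**Inputs.** From Procedures (RCT): 36 siblings, "randomly assigned to participate in Siblings FORWARD (N=18) or receive written materials about future planning (N=18"). Assumed, because the documents do not say: four race/ethnicity categories, their sizes, the effects and the completion counts. A 5% two-sided level is used throughout.

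**1. Same population, different codes.** Take groups of 18, 8, 6 and 4, true mean changes of 0, 1, 0 and 1 SD, and within-group SD 1.

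- Mean change = (8 + 4)/36 = 0.333. Between-group variance = (12/36)(24/36) = 0.222. Total variance = 1.222.
- The measure that ignores codes is eta = √(0.222/1.222) = 0.43.
- For any coding, r = cov(code, change)/√(var(code) × 1.222).
- Codes (1, 4, 2, 3): mean code = (18 + 32 + 12 + 12)/36 = 2.056; var = 206/36 − 2.056² = 1.497; cov = (32 + 12)/36 − 2.056 × 0.333 = 0.537. So r = 0.537/√(1.497 × 1.222) = +0.40.
- Codes (4, 1, 3, 2), the same order reversed: r = −0.40.
- Codes (2, 3, 4, 1): mean code = 88/36 = 2.444; var = 244/36 − 2.444² = 0.802; cov = (24 + 4)/36 − 2.444 × 0.333 = −0.037. So r = −0.037/√(0.802 × 1.222) = −0.04.

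Over all 24 codings r runs from −0.40 to +0.40, although the population is the same.

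**2. Power with one fixed coding.** Keep the sizes, code the groups 1 to 4, and let one group differ by 1.2 SD. The mean code is (18 + 16 + 18 + 16)/36 = 1.89 and its variance is 1.099. If group k, with share w, is the one that differs, cov = 1.2 × w × (k − 1.89) and r = cov/√(1.099 × [1 + 1.44 w(1 − w)]). Power is by simulation.

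| Group that differs | cov | r | Power, correlation | Power, one-way F test |
|---|---|---|---|---|
| 1 (n=18) | −0.533 | −0.44 | about 81% | about 83% |
| 2 (n=8) | 0.030 | 0.03 | about 3% | about 65% |
| 3 (n=6) | 0.222 | 0.19 | about 19% | about 54% |
| 4 (n=4) | 0.281 | 0.25 | about 33% | about 40% |

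The correlation nearly matches the F test when the group that differs is the large one at the end of the code range. It fails when that group's code (2) lies close to the mean code (1.89). With no true difference, the fixed coding rejects about 5% of the time.

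**3. Completion t-test.** A second assumed data set has groups of 16, 8, 7 and 5 with 14, 3, 6 and 4 completers. Over the 24 codings, t runs from −2.64 to +2.64 (p = 0.012 at the extremes, p = 0.94 at the smallest |t|), and 8 codings give p < 0.05. The chi-square test gives one answer: 7.83 on 3 df, p = 0.050, with cells small enough to prefer an exact test.

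**4. Binary check.** A two-level variable coded 0/1, 1/2, 1/0 or 5/9 gives |r| = 0.295 (p = 0.081) and |t| = 1.10 (p = 0.28) every time. Only the sign changes, with the reference level. The t-test p-value is close to the uncorrected chi-square p of 0.27.

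**The case against.** The strongest reply is that the plan is under-specified rather than wrong. It nowhere prescribes integer codes, and an analyst might use indicator variables or two groups, either of which removes the dependence on coding. Aim 2 shows that the authors know categorical characteristics need a different test. The analysis is preliminary, and the Measures introduction says baseline characteristics serve here to describe the sample, leaving moderators to larger work. All of this stands and limits the weight of the point. It does not remove it: Aim 3 names the methods, applies them to race/ethnicity, and does not say the variable will be recoded. Reducing it to two groups would also discard information.

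A reader might infer more than the documents support:

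- **That every categorical moderator is affected.** English as the primary language is naturally yes/no, and both methods are valid for it apart from a sign read against the reference level. Income, if banded, is ordered. The rest are counts or scale scores.
- **That false positives are inflated.** Under no true difference, at least one of the 24 codings reaches p < 0.05 in about 24% of samples. That matters only if someone searches over codings, which the plan does not propose.
- **That the correlation is nearly powerless.** The 3% figure is the worst of the four cases in the table.
- **That the completion result has no sound analysis.** Aim 2 covers it.
- **That the team has committed to reporting results by race/ethnicity.** The diversity statements in Sample & Recruitment and in Design Considerations concern the choice of Arc chapters.

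**Conclusion.** The point holds, for race/ethnicity only, and is minor. As written, Aim 3 applies to a nominal variable two methods whose results depend on arbitrary numbering once there are three or more categories. The change-score analysis has no valid alternative elsewhere in the plan; the completion comparison does, under Aim 2.

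In the assumed 18/8/6/4 example, r can lie anywhere from −0.40 to +0.40 against a coding-free 0.43. Power with codes 1 to 4 runs from about 3% to 81%, against about 40% to 83% for the F test. These figures rest on the assumed categories, sizes and effects; the dependence on coding needs only three or more categories entered as numbers. The example pools both arms. If the analysis were confined to the 18 siblings in the program arm, F-test power for a 1.2 SD difference in the second group would be only about 29% to 33%, depending on the assumed group sizes. No main comparison of the trial is touched.

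**What to change.** In the last paragraph of Data Analysis, Aim 3:

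- **Change scores.** Keep correlations for the ordered, continuous and binary characteristics. For race/ethnicity, compare mean change across pre-specified categories by one-way ANOVA or indicator variables with a stated reference category, and report category differences with 95% confidence intervals.
- **Completion status.** Use the Aim 2 approach: t-tests for continuous characteristics, and chi-square or Fisher's exact tests for categorical ones.

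This takes one or two sentences and no new data. Sparse categories may have to be combined in advance, and the multi-degree-of-freedom test will have low power at this sample size. The change cures the coding problem only: like the correlation it replaces, a one-way comparison of change has no arm-by-characteristic term, so it should still be described as exploratory.

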## Design Considerations & Future Directions

Our decision to focus on siblings (and exclude families without siblings) responds to the literature identifying siblings' preference to assume a greater role in their brother's/sister's planning and indicating that "family-centered" programs are perceived as focusing exclusively on parents. This allows us to tailor the program to siblings' unique role and ascertain program feasibility within this specific population. In the future,

we may expand the program to include families without eligible siblings; these families may enroll cousins, nieces/ nephews, close friends, etc. Our decision to enroll a heterogeneous sample across ASD severity, age, service needs, and extent of existing family planning follows from our strong desire to design a program that can be incorporated into community settings (which serve heterogeneous populations) in the future. We have attempted to make the materials and session goals flexible enough to be applied across varying ASD presentations and family situations. If successful, we expect that this model can be applied to other disability populations in addition to ASD. Similarly, our decision for community providers to deliver the program corresponds to our goal of incorporating community input from the outset and designing a program that can be feasibly implemented on a larger scale. We expect some provider turnover and are prepared to provide in-depth training to subsequent staff and to guide participants through therapeutic aspects of staff transition.

Based on conversations with state- and national-level Arc executives (see Support Letters), we plan to roll out

future iterations of the program on a much larger scale. The decision to exclusively utilize telehealth technology is due to the small nature of the study and our desire to make this novel delivery method universally applied. In future iterations of the program, we will likely give siblings the option of participating in person. Similarly, the focus on English-speaking families is also due to the small scope of the proposed project and limited resources. We plan to develop program materials in Spanish as a proximal follow-up to this proposed work, and we will incorporate Spanish language providers and/or interpreters into future trials. We have attempted to reduce disparities by taking a community-based approach and selecting Arc chapters with high diversity in terms of race, ethnicity, and income. The inclusion of the adult with ASD corresponds to attempts to develop truly person-centered future plans. We expect that the degree and nature of involvement of the adult with ASD will vary widely, and we will collect detailed feedback about how to increase their involvement as much as possible. Finally, the utilization of an information-only control condition corresponds to the current standard of care in which siblings are seldom involved in future planning at all. Additional future directions in subsequent, larger-scale trials include longer-term follow-up of participants to assess program efficacy and increased examination of mediators and moderators.

**Table 4: Timeline & Milestones**

Table 4: Timeline & Milestones		
Y1	Jan-Mar	
 
- Convene CAB to review qualitative goals
 
- Hire & train staff
 
- Finalize recruitment procedures
 

	Apr-June	
 
- Recruit & conduct focus groups/interviews with service providers (N=12-16), siblings (N=18-24), & adults with ASD (N=8)
 
- Analyze qualitative findings
 
- Finalize program manual by incorporating qualitative findings & CAB input
 
- Set up WebEx technology
 

	July-Dec	
 
- Provide in-depth training on program delivery to providers
 
- Conduct open trial (N=5)
 
- Provide ongoing, intensive consultation to community providers
 
- Collect, analyze, & iteratively implement feasibility & acceptability data from open trial participants & providers
 

Y2	Jan-Dec	
 
- Implement the RCT by enrolling ~2 families per month (24 siblings)
 
- Prepare conference papers & manuscripts from qualitative data
 

Y3	Jan-June	
 
- Continue RCT by enrolling ~2 families per month (12 additional siblings)
 

	July-Sept	
 
- Finish collecting 3-month follow-up data
 
- Offer Siblings FORWARD program to control siblings
 

	Oct-Dec	
 
- Collect post-program data for control sibs who later enrolled in Siblings FORWARD
 
- Conduct quantitative & qualitative analyses from RCT
 
- Revise and finalize program manual
 
- Prepare conference papers & manuscripts
 
- Prepare grant application for a larger-scale trial of the program
 

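### Table 4 closes 3-month follow-up before about 8 of 36 siblings reach Time 3, and leaves no time for the planned post-program data from controls

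*Combined protocol and SAP*

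**What the plan says.** Table 4 (Timeline & Milestones) gives the RCT calendar:

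- Year 2, January-December: "Implement the RCT by enrolling ~2 families per month (24 siblings").
- Year 3, January-June: "Continue RCT by enrolling ~2 families per month (12 additional siblings").
- Year 3, July-September: "Finish collecting 3-month follow-up data" and "Offer Siblings FORWARD program to control siblings".
- Year 3, October-December: "Collect post-program data for control sibs who later enrolled in Siblings FORWARD", together with the quantitative and "qualitative analyses from RCT".

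The RCT paragraph under Procedures fixes the visits. Controls complete "Time 3 measures 7 months after enrollment". Program siblings have six sessions over 4 months, then "complete Time 2 measures immediately after program completion, and complete Time 3 measures 3 months later". The Siblings FORWARD Program Description also gives a 4-month program.

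The Control Condition section makes the offer to controls wait until all outcome data from both groups have been collected. Data Analysis, Aim 3, plans one-way ANOVAs, pre to post program, in controls who then take it up. It handles missing data by last observation carried forward.

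**The concern.** These sections cannot all be followed. Enrollment to the end of June plus seven months runs into the following January, but Table 4 closes follow-up in September and analyzes in October-December. If no control may be offered the program until every Time 3 value is in, and the program takes four months, the post-program data cannot arrive in the window Table 4 gives them.

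The text does not say which date gives way, so the consequences are conditional:

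- **If Table 4's dates are kept,** late Time 3 values could be treated as missing and carried forward. For quality of life, which is measured only at Time 1 and Time 3, the carried value would be the baseline value. Alternatively, some controls could be offered the program before their own Time 3. Either could weaken the randomized 3-month comparison.
- **If the Control Condition rule is kept,** an analysis named in Aim 3 has no data within the calendar.

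**Working it through.** **Inputs.** Enrollment is 24 in Year 2 and 12 in January-June Year 3, about 2 per month (Table 4). Arms are 18 and 18, Time 3 is at 7 months, and the program lasts 4 months (Procedures; Program Description). Follow-up closes in September Year 3 and control post-program data close in December Year 3 (Table 4). Number the months from January Year 2 = 1, so June Year 3 = 18, September Year 3 = 21 and December Year 3 = 24. Accrual is assumed even.

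**1. Reproduce the plan's total.** 2 × 12 + 2 × 6 = 24 + 12 = 36, as stated.

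**2. Time 3 against the September close.** A sibling enrolled in month m reaches Time 3 in month m + 7.
- On time: m + 7 ≤ 21, so m ≤ 14 (February Year 3), giving 2 × 14 = 28.
- Late: m = 15 to 18, giving 2 × 4 = 8, and 8/36 = 22%. With 1:1 allocation, about 4 per arm are expected.
- The late visits fall 2 each in October, November and December Year 3 and January Year 4. The last 2 come after the calendar ends.
- Timing within the month matters little. The count is 8 with mid-month, end-of-month or spread enrollment. With enrollment on the first of each month it is 6 or 8, depending on whether 1 October counts as late.

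**3. Sensitivity to pace.** At a constant pace r per month, the number late is 36 − 14r.

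| Pace per month | Late |
|---|---|
| 2 | 8 |
| 2.25 | 4.5 |
| 2.5 | 1 |
| 36/14 = 2.57 | 0 |

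At 2.57 per month, Year 2 would enroll 12 × 2.57 ≈ 31, not 24. Keeping 24 in Year 2, the other 12 would all have to enroll in January-February Year 3, at 6 per month. A program arm that finished early would not help controls, whose visit is fixed at 7 months, so an expected 4 controls stay late.

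**4. Control post-program data under the Control Condition rule.** The last Time 3 is in month 18 + 7 = 25 (January Year 4). Adding the 4-month program gives month 29 (May Year 4), which is later than month 24. Controls with post-program data by December Year 3: 0 of 18.

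**5. What the December window requires.** A 4-month program ends by month 24 only if it starts by the end of month 20 (August Year 3). Even with every Time 3 value in on 30 September (month 21), it would end in month 25, late January Year 4. To meet both the rule and the window, the last enrollment must be by month 20 − 7 = 13 (January Year 3), a pace of 36/13 = 2.77 per month.

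**6. Following Table 4's dates alone.** At the end of August Year 3, siblings enrolled in months 14 to 18 have not reached Time 3: 5 × 2 = 10, of whom 5 are expected to be controls.

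**7. Illustration only.** If each control were offered the program at that sibling's own Time 3, finishing by December needs m + 7 + 4 ≤ 24, so m ≤ 13. That covers 26 siblings, an expected 13 of 18 controls. It is an expected value and assumes full retention and uptake and an immediate start. No section states this rule.

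**The case against.** The strongest reply is that Table 4 is a milestone table in a funding-stage plan and sets no data cut-off. Procedures define Time 3 per participant, so the natural course is to collect the late visits when they fall due. A visit due in October is not missing, so carrying forward would not be triggered. This stands in part: losing 22% of Time 3 values is a risk only if staff stop on the milestone date. It does not remove the conflict, because Table 4 also schedules the RCT analysis for October-December, before the last 2 visits.

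The stakes are also limited. This is a feasibility pilot, effect sizes are computed on pre-to-post change, and the plan of action is rated at Time 2. The analysis left without data is an uncontrolled look at controls who choose the program. All of that is correct, and it limits the seriousness of the point.

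Finally, Table 4 and the Control Condition section agree on the order: finish follow-up, then offer. Had follow-up closed in July or August, the December window could be met. That is true, but it needs enrollment to end by January Year 3, five months before Table 4's own close.

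**Conclusion.** The concern holds. At the stated average pace, 8 of 36 siblings (22%, about 4 per arm) reach Time 3 after the September Year 3 close, the last in January Year 4. Under the Control Condition rule as written, 0 of 18 controls can give post-program data by December Year 3; the first would come about May Year 4.

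The count of 8 rests on even accrual at 2 per month and falls to zero at 2.57. The zero rests on reading the offer rule as trial-wide, which its reference to both groups supports, and on a 4-month program. The effects on the 3-month comparison are possible, not certain. The randomized Time 1 to Time 2 effect sizes are not touched. The plan should be corrected, but the main comparison does not depend on it.

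**What to change.** Reconcile Procedures, the Program Description, Control Condition, Aim 3 and Table 4:

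1. Restate Table 4 so that Time 3 collection runs to seven months after the last enrollment (January Year 4 at the stated pace), with the final RCT analysis after it. Late Time 3 values are then collected, not carried forward.
2. Reconcile the Control Condition offer rule with Table 4's offer and post-program rows. Keep what that rule already implies: no control is offered the program before that sibling's own Time 3. The choice of rule beyond that is the sponsor's.
3. State in Aim 3 how many controls the reconciled calendar is expected to supply for the pre-to-post analysis, or that the analysis falls outside the calendar.

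**Cost.** These are date and wording changes, but follow-up and final analysis run past December Year 3, the end of the only calendar given. If the reconciled text lets controls start while the RCT is still running, providers would serve both groups at once, with 5 loan tablets budgeted for those who need them. Controls still awaiting Time 3 might also hear of the content, since recruitment is mainly through two chapters.

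**Alternative.** Ending enrollment by February Year 3 needs 2.57 per month and cures only the Time 3 overrun. Meeting the post-program window as well needs enrollment to end by January Year 3, at 2.77 per month.
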